### **6.6.9 Study drug discontinuation**

Study drug must be discontinued for a given patient if the investigator determines that continuing it would result in a significant safety risk for that patient. The following laboratory abnormalities **require** study drug discontinuation:

- above-normal BUN (40mg/dl or greater) following an earlier result within the normal range
- above-normal creatinine (2mg/dl or greater) following an earlier result within the normal range

In addition, the study drug has to be discontinued on any sign of hypersensitivity against Tobramycin and on signs of oto- or nephrotoxicity. In case of oto- or nephrotoxicity, an assessment of Tobramycin serum level is recommended. If the level is fallen below 2 $\mu$ g/ml, a restart of study drug may be considered by the investigator. A therapeutic drug monitoring should be initiated in patients with a history of any renal dysfunction and study drug has to be discontinued if the Tobramycin serum level exceeds 12 $\mu$ g/ml.

The last date of study drug intake should be entered into the Study Completion CRF and the reason for discontinuing study drug should be given on the comments page. If a patient who discontinued study drug therapy performed all scheduled study procedures and measurements, he will be counted as a study completer.

### **6.6.10 Emergency unblinding of treatment assignment**

Not applicable. This study has an open-label design.

### **6.6.11 Study completion and post-study treatment**

The study will be considered completed for an individual patient when he/she completes Study Visit 5. After this date, any SAEs occurring in this patient for the following 30 days will be reported (see Section 8.2). The investigator will follow-up any AEs ongoing or for which no final outcome can be reported at the termination visit. Pregnancies will be followed-up until birth (see Section 8.3).

The study as a whole will be completed once the clinical data base has been locked. It is intended that 35 patients will be recruited. Recruitment into the study is to be terminated by the sponsor once the targeted number of patients who start the study treatment has been met or is foreseen to be met with the patients already in screening. Any patient already in the screening phase at the time of termination of recruitment can still undergo the start of study processes.

After premature withdrawal Study Visit as designated for end of study should be scheduled as soon as possible.

The study can be terminated for reasons stipulated in the study contract. Should this be necessary, the patients should be contacted and scheduled for their end of study assessments as described in Section 7. Novartis will be responsible for informing IRBs and/or IECs of the early termination of the study.

## 7 Visit schedule and assessments

Table 7-1 lists all of the assessments and indicates with an “X” the visits when they are performed.

Patients should be seen for all visits on the designated day as shown in Table 7-1.

Patients who discontinue study drug therapy before completing the study, and those who prematurely withdraw from the study for any reason, should be scheduled for a visit as soon as possible, at which time all of the assessments listed for the final visit (visit 5) will be performed.

If they refuse to return for these assessments or are unable to do so, every effort should be made to contact them or a knowledgeable informant by telephone to determine at a minimum the safety evaluations during the 30 days following the last dose of study drug therapy, including final contact at the 30-day point. Documentation of attempts to contact the patient should be recorded in the patient record.

All data obtained from the assessments listed in Table 7.1 and described in detail in the subsections below must be supported in the patient’s source documentation.

**Table 7-1 Assessment schedule**

Visit	1	2	3	4	5*
Procedure	-26 to -5 Screening	1 Baseline	7 Week 1 (+/- 2 days)	28 Week 4 (- 3 days)	56 End of Study (- 3 days)
Inclusion / exclusion criteria	x	x			
Demographic data	x				
Obtain informed consent	x				
Physical examination	x	x			x
Vital signs	x	x	x	x	x
Height and weight / BMI	x	x	x	x	x
Clinical chemistry a	x				x
Sputum (microbiology) b	x	x	x	x	x
Lung function (spirometry) c	x	x	x	x	x
FRC (bodyplethysmography)		x	x	x	x
LCI/ MBW	x	x	x	x	x
Serum pregnancy test	x				x
Urine pregnancy test		x			
Adverse events		x	x	x	x
Serious Adverse events	x	x	x	x	x
Concomitant medication	x	x	x	x	x

\*When a patient prematurely discontinues the study before study completion, all procedures at Visit 5 should be performed.

- Clinical chemistry: urea, creatinine, CRP
- Pre-treatment sputum to be collected, preferably the first morning specimen; if the patient is unable to produce a sputum specimen, a deep cough throat swab or an induced sputum sample will be collected, at the investigator's discretion.
- Spirometry should be done using a bodyplethysmograph to allow for FRCples assessment in parallel

At screening (Visit 1), for patients who have consented to study participation, or on whose behalf informed consent has been obtained and who have assented to study participation, the following will be recorded: patient demographics, concomitant medication, the results from a physical examination including height and weight, Spirometry (FEV1), vital signs and LCI/ MBW. Blood, will be collected for serum pregnancy test (where applicable) and for safety laboratory testing. Sputum (or deep throat cough swabs, where applicable) will be collected to assess *Burkholderia cenocepacia complex* in all patients and *Pseudomonas aeruginosa* in patients for whom only one positive sputum culture in the year before screening is documented.

Following the screening period, the eligible patients who meet all inclusion/exclusion criteria will be enrolled in the study. All screening safety evaluation results must be available prior to enrollment. Sputum sampling at Baseline (V2) will be conducted before first inhalation of Study drug in the current treatment cycle to collect the baseline values. Thus, it is recommended to schedule visit 2 early in the morning. If this is not possible, Sputum can be collected by the patient at home before first inhalation (either in the evening the day before

V2 or on the day of V2 in the morning before first inhalation). Spirometric and LCI/MBW measurements will be conducted before or at least 1h after inhalation of Study drug, measurements should start with LCI/MBW followed by spirometry after a delay of at least 15 minutes.

Urine sampling for pregnancy testing will be conducted where applicable. A physical examination will be performed, vital signs and concomitant medication will be recorded. Height, and weight and Body mass Index (BMI) will be recorded.

Visit 3 will take place one week after baseline visit (+/- 2 days). Sputum sampling will be conducted before inhalation of antibiotics or at least 10h after. LCI/MBW and Spirometric measurements will be conducted before or at least 1h after inhalation of Study drug, measurements should start with LCI/MBW followed by spirometry after a delay of at least 15 minutes. Clinical signs and symptoms, BMI, height and weight, vital signs, concomitant medications, adverse events and assessment of dosing frequency and compliance will be recorded.

Visit 4 will take place 4 weeks after baseline visit at the last day of the on-cycle (- 3 days) but not thereafter. Sputum sampling will be conducted before inhalation of antibiotics or at least 10h after. Spirometric and LCI/MBW measurements will be conducted before or at least 1h after inhalation of Study drug, measurements should start with LCI/MBW followed by spirometry after a delay of at least 15 minutes. Vital signs, BMI, height and weight will be recorded. Following Visit 4, patients will enter the off-treatment period for 28 days (no antibiotics inhalation, but standard care maintained).

**Completion/Termination:** Patients return for a completion visit on the last day of the 28 days off-treatment period (- 3 days) but not thereafter (Visit 5). The required procedures are a physical examination including recording of height and weight, BMI, vital signs, spirometry and LCI/MBW measurement (starting with LCI/MBW followed by spirometry with a delay of at least 15 minutes), and recording of adverse events and concomitant medications. Blood, sputum (or deep throat cough swabs, where applicable), will be collected for safety laboratory testing and serum pregnancy test (where applicable).

If the patient terminates early from the study, all examinations of Visit 5 should be performed as a discontinuation visit. Reasons for discontinuations should be captured in the source documentation and by fully completing the relevant CRF Form sections with all information available to the investigator.

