**Table 6-2 Washout of prohibited treatment and study treatment/concomitant medication prior to study visits**

Treatment/medication	Wash-out time	Timepoint	Remarks
SABA	6hours (h)	Prior to FEV1/LCI Assessment	
LABA / LAMA	12h	Prior to FEV1/LCI Assessment	
iv/oral Antibiotics	allowed in on-Phase + 5 Days in following off	Prior to Visit 5	Inhalation of Tobramycin stopped for more than 3 days: Discontinue the study
iv/oral Antibiotics	28 days	Prior to Visit 2	
Inhalation of Tobramycin	1h	Prior to FEV1/LCI Assessment	
Inhalation of Tobramycin	10h	Prior to sputum sampling (Sputum may be collected at home prior to visit)	Example for V3/4: Sputum sampling at home followed by Inhalation. Visit 4 on the next day.
Inhalation of Colistin or Aztreonam	56 days	Prior to visit 2	
Change in physiotherapy or inhalative concomitant medication, eg macrolides or steroids	56 days	Prior to visit 2	Macrolides, physiotherapy, pulmozyme, hypertonic saline, bronchitol, steroids, bronchodilators. Stable treatment is allowed.
Any other study drug	30 days	Prior to visit 1	30 days or 5x T 1/2, whichever is longer

The following treatments **are permitted** between start of the study drug administration and completion/termination and should be accurately documented in the CRF:

- Anti-pseudomonal antibiotics
  - Intravenous or oral Anti-pseudomonal antibiotics are allowed for the treatment of Pulmonary exacerbation during the on-phase as needed by patient condition if i.v. treatment is completed 5 days latest after the end of the on-phase.
  - If patients are prescribed i.v. aminoglycosides for symptoms of pulmonary exacerbation, continuation of inhalation of Study drug is at the investigator's discretion.
    - If inhalation of Study drug is continued during i.v. aminoglycoside therapy, patients will continue with the study schedule for the remainder of the study; however, therapeutic drug monitoring is strongly recommended with appropriate modification of the i.v. aminoglycoside dose as necessary;
    - Inhalation of antibiotics can be interrupted during i.v. aminoglycoside therapy (eg. due to elevated serum levels of study drug) for a maximum of 3 days. Patients should restart inhalation of antibiotics in order to complete the 28 days cycle as close as possible to their initial study schedule.
  - Pre-planned anti-pseudomonal antibiotics (i.v.) in the absence of an AE (prophylaxis of Pulmonary exacerbation) are not permitted during the study and 28 days prior Baseline Visit (V2)

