CF Patients chronically infected with *P. aeruginosa* on regular antipseudomonal standard inhalation therapy in an on / off regimen are showing well characterized differences in FEV1 between on and off-cycles (Ramsey et al 1999; Konstan et al 2011a). Thus, this population allows an evaluation of LCI based on these intraindividually observed FEV1 alterations, without any changes to their standard therapy.

The microbiology parameter “colony forming units” of pseudomonas aeruginosa has been selected as a third efficacy marker to be compared with LCI as well, because spirometry (FEV1) strongly depends on daily performance and compliance to spirometry of the patient. LCI and FEV1, respectively, should reflect alterations in bacterial colonization.

The study duration of 8 weeks comprises a complete on / off treatment cycle starting with 28 days inhalation followed by 28 days without Study drug inhalation. This design allows to obtain baseline lung function at start of the inhalation cycle (representing minimal lung function at the end of the inhalation pause), the development/improvement of lung function after 1 and after 4 weeks of inhalation therapy (representing maximal lung function) and the subsequent decline in lung function after 4 weeks of cessation of inhalation therapy. The detected intraindividual differences between best and worst lung function then allow to compare LCI and FEV1 results and to assess feasibility of LCI as primary surrogate outcome parameter in future clinical studies.

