2.1.1 General definitions

Study treatment/ Study drug: The investigational drug whose properties are being tested in the study.

Date of first administration of study drug/treatment: It is defined as the date of first dose of study drug administration to the patient.

Date of last administration of study drug/treatment: It is defined as the date of last dose of study drug administration to the patient.

Study day: Study day is defined as the number of days since the date of first dose of study drug administration. For a particular date, study day is calculated as:

Study day = Assessment date – Date of first dose of study drug administration + 1.

Baseline: Baseline is the last assessment obtained on or before the date of first dose of study drug administration. All assessments obtained after the date of first dose of study drug administration are considered as post-baseline unless otherwise specified.

On-treatment period: The period where the patients are exposed to the study treatment. For this study the treatment phase consists of 28 days of on-treatment period.

Lost to follow-up: The patients whose study completion status is unclear because they fail to appear for study visits without stating an intention to withdraw.

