2.5.2 Statistical hypothesis, model, and method of analysis

The primary objective of the study is to evaluate the effectiveness of antibiotic therapy TBM100 in patients with CF aged 6 years and older with mild to moderate lung disease. The effectiveness will be assessed by changes in LCI from baseline to Week 4. Baseline LCI is the assessment taken prior to the start of TBM100, which is typically the value at Visit 2. If baseline value is missing then change is taken from the data recorded at screening. The primary analysis will include patients with a valid observation at baseline and post-baseline visit.

The summary of LCI at baseline, at each post-baseline visit and its change from baseline to each post-baseline visit will be presented using descriptive statistics (n, mean, standard deviation, median, minimum and maximum). Change from baseline will be calculated as value at post-baseline visit minus value at baseline.

Between visits comparison for changes in LCI from baseline will be analyzed using an ANOVA model with factors patient and visit. Estimates over time will be presented as LS-Means, pairwise LS-Mean differences along with 95% confidence intervals and two sided p-values for the pairwise differences between visits.

Additionally, for assessing trend of change in LCI over time, mean values over time and the raw LCI values over time for each patient will be displayed graphically for each respective visit. All analysis mentioned in this section will be done for safety set at 5% significance level.

All efficacy data will be listed with date of assessment by age group and treatment dose form.

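### Visit 2 LCI and FEV1 may be measured after the first tobramycin inhalation of the cycle, against the plan's own pre-drug baseline, and the SAP does not screen such values out

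*Protocol*

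**What the plan says.** **Timing of measurement.** The Visit 2 and Visit 4 paragraphs of protocol section 7 carry the same sentence: "Spirometric and LCI/MBW measurements will be conducted before or at least 1h after inhalation of Study drug". The Visit 3 paragraph says the same: "LCI/MBW and Spirometric measurements will be conducted before or at least 1h after inhalation of Study drug". Table 6-2 lists a 1 h gap for inhaled tobramycin, with the timepoint given as "Prior to FEV1/LCI Assessment" and no exception for Visit 2.

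**Sputum is treated differently.** "Sputum sampling at Baseline (V2) will be conducted before first inhalation of Study drug in the current treatment cycle to collect the baseline values". If an early visit is not possible, the patient may collect sputum at home, either the evening before or "on the day of V2 in the morning before first inhalation". The protocol thus foresees that a patient may arrive at Visit 2 already dosed.

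**Meaning of baseline.** Protocol section 11 describes baseline lung function as "representing minimal lung function at the end of the inhalation pause". SAP 2.5.2 says "Baseline LCI is the assessment taken prior to the start of TBM100", and adds that this is typically the Visit 2 value. SAP 2.1.1 is looser: "Baseline is the last assessment obtained on or before the date of first dose of study drug administration". SAP 2.7.1.5 takes Visit 2 as baseline, and the model code in SAP 5.4.1 selects readings by visit number (2 to 5).

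**The concern.** The trial uses one on/off cycle to see whether LCI registers the 28-day effect of inhaled tobramycin. That requires an off-drug baseline. A reading an hour or more after the first dose carries any acute effect of that inhalation, such as airway irritation or clearance. It fails the definitions in protocol section 11 and SAP 2.5.2, yet passes SAP 2.1.1 and enters the primary model.

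At Visits 3 and 4 a patient may be measured before or after that session's dose, and no visible passage keeps this relation the same from visit to visit. Visit 5 is off-drug by schedule, so an acute effect can enter only the Visit 4 side of the Week 4 versus Week 8 comparison. LCI and FEV1 need not respond alike to an inhalation, so the comparison of the two methods could be affected too.

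The plan controls dose timing elsewhere. Sputum at Visits 3 and 4 must be pre-dose or at least 10 h post-dose. Section 6.6.8 asks for consistent timing of hypertonic saline. Section 7.4.1 rules out a next-day repeat of the Visit 5 washout once inhalation has restarted. Lung function at Visit 2 has no matching safeguard.

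**Working it through.** 1. **The plan's own figure.** Protocol 10.7 assumes an FEV1 change of 5% with an intraindividual SD of 9%, 80% power and two-sided 5%. A paired t-test on the change gives power 0.794 at n = 27 and 0.809 at n = 28, so the stated 28 reproduces. The target of 35 corresponds to 28 / (1 − 0.20) = 35. This point disputes neither number.

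2. **Does a post-dose Visit 2 reading count as baseline?**
   - Protocol section 7 and Table 6-2: permitted from 1 h after inhalation.
   - Protocol section 11: no, because the pause has ended.
   - SAP 2.5.2: no, because drug has started.
   - SAP 2.1.1: yes, because the date is the date of first dose.
   - SAP 2.7.1.5 and 5.4.1: yes, because it is a Visit 2 value.
   - The model has no term for time since dose, and SAP 2.5.4 plans no supportive analysis.

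3. **Form of the bias.** Let d be the acute post-dose shift (assumed equal at each visit) and qv the share of readings at visit v taken post-dose. The expected mean at visit v is its dose-free mean plus d × qv. Hence:
   - Week 4 minus baseline: bias = d × (q4 − q2), which is zero if q4 = q2.
   - Week 4 minus Week 8: bias = d × (q4 − q5) = d × q4, because q5 = 0.

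4. **Illustration for FEV1.** The documents give no d and no q. Assume |d| from 0 to 3 points on the scale of the 5% change, in either direction, and q4 = 0.5. The Week 4 versus Week 8 bias then runs from 0 × 0.5 = 0 to 3 × 0.5 = 1.5 points. At the top of that range this is 1.5 / 5 = 30% of the expected change. The Week 4 minus baseline contrast would reach 1.5 points only if q2 and q4 differed by 50 percentage points.

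5. **What this would do to power at n = 28 (FEV1, assumed values).** Suppose half the Visit 2 readings are post-dose and all Visit 4 readings are pre-dose. The mean change is 5 − 0.5d and the SD is √(81 + 0.25d²).

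| d | Mean change | SD | Power |
|---|---|---|---|
| +2 | 4.0 | 9.055 | 0.616 |
| +1 | 4.5 | 9.014 | 0.721 |
| 0 | 5.0 | 9 | 0.809 |
| −1 | 5.5 | 9.014 | 0.875 |
| −2 | 6.0 | 9.055 | 0.922 |

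A negative d raises power only by inflating the estimated change.

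6. **Equal shares at Visits 2 and 4.** With q2 = q4 = 0.5, independent between visits, and |d| = 3, the mean is unbiased. The SD is √(81 + 2 × 0.25 × 9) = 9.247 and power is 0.788. The harm comes from imbalance between visits, not from mixing alone.

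7. **LCI.** The documents give no expected LCI change or SD, so no LCI figure follows.

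**The case against.** The rule is permissive, and several provisions push towards consistent timing. Section 7.5.3 has vital signs taken before inhalation during the treatment period, and Table 7-1 schedules them at Visits 2, 3 and 4; on a plain reading patients would usually arrive before that session's dose. Section 7.4.2 asks for spirometry at the same time of day within 1 h, and the washout test precedes spirometry, so with twice-daily dosing a patient's relation to the dose should tend to be similar across visits. Section 7 recommends an early-morning Visit 2. The 1 h gap is itself a deliberate washout.

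These controls stand, but only in part. The vital-signs rule does not govern lung function and sits beside an explicit provision for dosing at home on the morning of Visit 2. The time-of-day rule concerns the clock, not the interval since dose, and its alternative of any time after 11:00 loosens it further.

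A reader might infer that the on/off contrast does mix post-dose and pre-dose readings, that Week 4 versus Week 8 is always biased, or that a known part of the effect is lost. The documents support none of these. They do not say how many readings would be post-dose, the Week 4 versus Week 8 bias is zero if q4 = 0, and d is not given. A pre-dose reading at Visit 3 or 4 is still within the on-cycle; it only precedes that session's dose.

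Three steps of section 7.4.1 are redacted, and the washout SOP and the CRF are not among the documents, so further timing control or a recorded inhalation time may exist there.

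**Conclusion.** The point holds as an inconsistency in the baseline definition. Protocol section 7 and Table 6-2 permit a Visit 2 reading that section 11 and SAP 2.5.2 do not regard as baseline, while SAP 2.1.1, 2.7.1.5 and 5.4.1 would use it as one. Confidence in that reading of the text is high.

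That the results would be materially biased is not established. Size and direction depend on d and on the post-dose shares, both unknown, and the FEV1 figures above are assumption-driven. The Visit 3 and 4 part is weaker than the Visit 2 part, because partial controls exist and the primary contrast is unbiased in the mean when the shares at Visits 2 and 4 match. The matter still deserves correction: it touches the primary variable, and unless inhalation times are captured somewhere it could be neither detected nor adjusted for afterwards.

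**What to change.** - **Protocol.** Reconcile the Visit 2 lung-function sentence in section 7 and the tobramycin row of Table 6-2 with the sputum rule, section 11 and the SAP definitions, so that the Visit 2 measurement rule meets the plan's own pre-drug baseline. This concerns when readings are taken; prescribed dosing stays as it is.
- **Data.** Record the time of the last inhalation with each LCI and FEV1 reading, if the CRF does not already capture it.
- **SAP baseline.** For LCI and FEV1, replace the date-based definition in 2.1.1 with the one in 2.5.2. Flag Visit 2 values taken after the first inhalation as not meeting it, and state whether the fallback to the screening value in 2.5.2 applies to them.
- **SAP analyses.** Add one sensitivity analysis that excludes flagged Visit 2 values and one by pre-dose or post-dose status at Visits 3 and 4.

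The cost is protocol and SAP wording, possibly one CRF field, and a little more analysis. A few baseline values may drop out of the sensitivity analysis, with some loss of precision there.

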- MBW's at Visits 3 and 4 have to be repeated within 5 days after initial measurement or the patient has to be withdrawn.
- MBW at Visit 5 cannot be repeated on the following day if the patient has already restarted inhalation of Tobramycin in the new treatment cycle.

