## **9.3 Database management and quality control**

A clinical research organization (CRO) working on behalf of Novartis reviews the CRFs entered by investigational staff for completeness and accuracy and instruct the site personnel to make any required corrections or additions. Queries are sent to the investigational site using an

electronic data query. Designated investigator site staff is required to respond to the query and confirm or correct the data.

Concomitant medications entered into the database will be coded using the WHO Drug Reference List, which employs the Anatomical Therapeutic Chemical classification system. Medical history/current medical conditions and adverse events will be coded using the Medical dictionary for regulatory activities (MedDRA) terminology.

Spirometry data and LCI will be entered on the CRF by the site and transferred to Novartis. MBW plots will be transferred by Fax or secure email to the central MBW specialist. Central laboratory data will be transferred electronically to Novartis using an agreed Data Transfer Specification.

At the conclusion of the study, the occurrence of any protocol violations will be determined. After these actions have been completed and the database has been declared to be complete and accurate, it will be locked and made available for data analysis. Any changes to the database after that time can only be made by joint written agreement between the Trial Statistician and Statistical Reporting and the Clinical Trial Leader.

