5.5 Rule of exclusion criteria of analysis sets

All protocol deviations defined at the start of the study are listed with associated population codes in below table.

Deviation code	Text description	Severity code
INCL01	Patient has not provided the written informed consent.	1
INCL02	Cystic fibrosis diagnosis is not confirmed by the study protocol specified tests.	0

INCL03	Patient age is outside protocol specified range. Please verify Birth Year and Informed Consent date.	0
INCL04	Elevated LCI is < 7.5 at screening, confirmed by a central MBW specialist.	0
INCL05	FEV1 of < 50% predicted at screening.	0
INCL06	P. aeruginosa is not present in two sputum or deep cough throat swab cultures or bronchoalveolar lavage (BAL) (only for BAL, a threshold level of 103 CFU/mL is required) within 12 months prior to screening or in one culture within 12 months prior to screening and in the sputum or deep cough throat swab culture at screening	0
INCL07	No use of inhaled Tobramycin in 28 days on / off regimen in the past 3 months before screening.	0
INCL08	Patient is not clinically stable in the opinion of the investigator and unlikely to be able to participate in the study until the end of the study (Visit 5).	0
EXCL01	History of sputum culture or deep cough throat swab (or BAL) culture yielding Burkholderia cenocepacia complex within 2 years prior to screening and / or sputum culture yielding B. cenocepacia complex at screening (Visit 1).	0
EXCL02	Hemoptysis more than 60 mL at any time within 30 days prior to screening (Visit 1).	0
EXCL03	Patient has history of hearing loss or chronic tinnitus.	0
EXCL04	Serum creatinine 2mg/dL or greater, BUN 40 mg/dL or greater, known local or systemic hypersensitivity to aminoglycosides.	0
EXCL05	Patients who are regularly receiving more than 1 class of inhaled anti-pseudomonal antibiotic during the study or in the past 56 days (8 weeks) prior to baseline visit (Visit 2).	0
EXCL06	Patients who have used oral or intravenous anti-pseudomonal antibiotics within 28 days prior to on-phase of study drug (Visit 2). These patients may be rescreened after 1 month following stop of i.v. treatment.	0
EXCL07	Change in dose, formulation or strength of the study drug in the past treatment cycle before screening.	0

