OTH10	Spirometry was not conducted according to ATS criteria.	0
Med	Patient did not receive at least one dose of study drug	1

6 Reference

Not Applicable.

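### A repeated Visit 4 MBW can fall in the off-phase and still be analysed as Week 4 LCI, and the SAP's screening fallback for baseline is absent from the primary model code

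*Protocol*

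**What the plan says.** **Visit 4.** Protocol section 7 states: "Visit 4 will take place 4 weeks after baseline visit at the last day of the on-cycle (- 3 days) but not thereafter". It continues: "Following Visit 4, patients will enter the off-treatment period for 28 days". Section 7.4.1 deals with MBW that the central specialist judges inadequate. Measurements "at Visits 3 and 4 have to be repeated within 5 days after initial measurement or the patient has to be withdrawn". For the end of the study it does add a treatment-phase condition: "MBW at Visit 5 cannot be repeated on the following day if the patient has already restarted inhalation of Tobramycin". Section 9.3 describes how the specialist receives the data: "MBW plots will be transferred by Fax or secure email to the central MBW specialist". No turnaround time is given.

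The model code in SAP 5.4.1 selects records by visit number (2, 3, 4, 5). SAP 5.5 says of its list: "All protocol deviations defined at the start of the study are listed with associated population codes in below table". The list has a spirometry entry ("Spirometry was not conducted according to ATS criteria") but nothing on MBW repeats or visit windows.

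**Baseline.** SAP 2.1.1 defines it generally: "Baseline is the last assessment obtained on or before the date of first dose of study drug administration". SAP 2.5.2 uses the LCI value before the start of drug, typically Visit 2, and screening if that is missing. SAP 2.7.1.5, 2.13.1.1, 2.13.1.3 and 2.13.1.4 use Visit 2, and screening if missing. The code in SAP 5.4.1 leaves screening out. SAP section 4 lists two changes from the protocol, and the fallback is not one of them. In Protocol Table 7-1, plethysmographic FRC is first scheduled at Visit 2.

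**The concern.** Protocol section 11 rests the comparison of LCI with FEV1 on the contrast between the end of the pause and the end of the on-phase. A Visit 4 LCI taken during the next pause no longer measures the end of the on-phase, yet a site that follows section 7.4.1 can produce one and the SAP will treat it as the primary Week 4 value. No passage requires spirometry or sputum to be repeated with the MBW, so this LCI may be paired with on-phase FEV1 and CFU in the Week 4 comparison and correlation. Any dilution would then fall on LCI alone, which is the measure the study hopes to show is more sensitive.

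For baseline, a patient without a Visit 2 LCI could have a change in the summary tables and correlations that the primary model never uses. That change would start from a screening value taken on Day -26 to Day -5, not at the end of the pause.

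**Working it through.** **1. Days on which a repeat can fall.** Inputs: Visit 4 on Day 25-28 (Table 7-1); repeat up to 5 days later (section 7.4.1); on-cycle assumed to end on Day 28.

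| Visit 4 | Later-day repeat | Off-phase days |
|---|---|---|
| Day 25 | 26-30 | 29-30 (2 of 5) |
| Day 26 | 27-31 | 29-31 (3 of 5) |
| Day 27 | 28-32 | 29-32 (4 of 5) |
| Day 28 | 29-33 | 29-33 (5 of 5) |

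That is 14 of 20 later-day combinations (70%), or 14 of 24 (58%) when same-day repeats are counted. These are counts of possibilities, not probabilities. For Visit 3, the window is Day 5-9 and 9 + 5 = 14, so a repeat can be as late as Day 14.

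**2. The plan's own sample size.** Protocol 10.7 gives an FEV1 change of 5%, SD 9%, 80% power and two-sided 5%. A paired t-test (noncentral t) with 9% as the SD of the difference has noncentrality (5/9) x sqrt(28) = 2.94 and power 80.9% at n = 28 (79.4% at n = 27). So 28 reproduces, and 28/0.80 = 35. The documents give no effect or SD for LCI, so this FEV1 scale is borrowed below.

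**3. Dilution at Week 4.** Share of mean effect lost = p x f, where p is the share of patients with an off-phase repeat (assumed 5%-20%) and f is the share of that patient's effect lost at the repeat, on off-phase day 1-5.
- Linear loss over 28 days: f = 1/28 = 3.6% to 5/28 = 17.9%. Then p x f = 0.05 x 1/28 = 0.18% to 0.20 x 5/28 = 3.57%. Times 2.94, this is 0.005 to 0.105 standard errors. Power with effect (5/9)(1 - p x f) and the SD held is 80.8% to 78.0%.
- Half-life 7 days: f = 1 - 2^(-1/7) = 9.4% to 1 - 2^(-5/7) = 39.0%. Then p x f = 0.47% to 7.81%, and power is 80.5% to 74.3%.
- Stress case, complete reversion in 20% of patients: mean 5 x 0.8 = 4.0, SD = sqrt(81 + 0.2 x 0.8 x 25) = 9.22, bias 0.59 standard errors, power 60.0%.

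**4. Screening as baseline.** Day -26 to Day -5 is 26 to 5 days before Day 1 if there is no Day 0. Under the same linear assumption, the screening value misses 26/28 to 5/28 of the decline that Visit 2 would show. One such patient among 28 lowers the mean change by (1/28)(26/28) = 3.3% to (1/28)(5/28) = 0.6%. This reaches tables, correlations and exploratory changes only, because the primary code drops screening.

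**5. Cost of excluding flagged patients.** Leaving out 6 of 28 gives n = 22 and power 70.0% at 5/9.

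**The case against.** Much can be said in defence, and it limits the point.

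- A reader might infer that late repeats would go unseen. They would not: SAP 2.5.2 and 2.7.1.5 list efficacy data with assessment dates, and SAP 2.4.1 lists dosing dates. What is missing is an analysis rule that uses those dates.
- A reader might infer that only MBW is repeated, so that FEV1 certainly stays on-phase. The documents are silent. A mismatch is possible, not established.
- A reader might take 70% as the off-phase share of repeats. It omits same-day repeats. It also treats Day 28 as the last on-cycle day, although Protocol 6.6.8 lets patients who interrupt inhalation complete the cycle near, not exactly on, schedule.
- A late quality verdict is an inference from the transfer route. The same-day requirement at Visit 2 suggests that quick verdicts are feasible, and the detailed measurement steps are redacted.
- A reader might see several conflicting baselines. The texts in SAP 2.1.1, 2.5.2, 2.7.1.5 and 2.13 normally yield the same value, and SAP 2.1 lets specific rules override general ones. Only the code differs. Even there, the restriction in SAP 2.5.2 to patients with a valid baseline could be applied when the input dataset is built.
- Protocol section 7 allows Visit 2 LCI at least 1 h after inhalation, which could suggest a biased baseline. The same allowance holds at Visits 3 and 4, and the documents support no claim of bias.
- Spirometry at Visit 1 may be done on a plethysmograph, so a screening FRC might exist; it is simply not scheduled.

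What stands is the Visit 4 conflict, the missing analysis rule, and the mismatch between the SAP's fallback and its code.

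**Conclusion.** The point holds and is minor. Following the protocol as written can put an off-phase LCI into the primary Week 4 value, and no rule says how to analyse it. The alternative of withdrawal is stated, so an off-phase repeat is permitted but not inevitable. The expected direction is dilution. The effect is probably small: at most 3.6% of the mean effect under linear loss with up to 20% off-phase repeats, and 7.8% with a 7-day half-life. It is not small if LCI reverts completely within days in a fifth of patients. Repeat rate, decay and LCI variance are all missing from the documents, so confidence is high in the textual conflict and limited on its impact.

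The baseline mismatch should affect few patients, because Protocol 7.4.1 withdraws those whose inadequate Visit 2 MBW cannot be repeated the same day. It does not enter the coded primary model. The planned sample size is unaffected.

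**What to change.** 1. Reconcile the Visit 4 timing in Protocol section 7 with the repeat rule in section 7.4.1. Which rule should prevail is for the sponsor and investigators.
2. In the SAP, flag Visit 4 LCI values dated after the patient's last on-cycle day and Visit 3 values outside Day 5-9. Keep them in the main analysis and add one sensitivity analysis that excludes them. A deviation code is not needed for a repeat that the protocol itself requires.
3. Use Visit 2 as the single efficacy baseline in SAP 2.1.1, 2.5.2, 2.7.1.5, 2.13 and the code. Remove the screening fallback from change and correlation analyses; if it is kept as a sensitivity analysis, list it in SAP section 4. Delete it for air trapping. The laboratory fallback is a separate matter, since Table 7-1 schedules clinical chemistry at Visits 1 and 5 only.

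The cost is a protocol clarification, short SAP edits, a derived flag from dates already collected and one extra model run. A few changes from baseline become missing. The sensitivity run has less power (70.0% if 6 of 28 patients are excluded), so it supports the main analysis and does not replace it.
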